The Evaluation Of The Efficiency Of Micro-osteoperforation

Date :April 28, 2016

Statistical Analysis Plan (SAP)

Data were analyzed by IBM SPSS (version: 25.0, IBM Corp., Armonk, New York, USA) statistical package program. Descriptive statistical data were number of units (n), percentage (%), mean \pm standard deviation ($\bar{x} \pm$).

Correlation between the measurements (method error) was evaluated with intraclass correlation coefficient. In the assessment of the compatibility of the Model and Little perpendicularity index measurements, the intraclass correlation coefficient was specified with a 95% confidence interval.

The normal distribution of the numerical variables was evaluated by Shapiro-Wilks normality test and Q-Q graphs. Independent samples t test was used to compare the means between two independent groups of continuous measurements, and dependent sample t test was used to compare two dependent groups. Gender distribution between groups was evaluated using chi-square test.

The comparison of the groups according to time was made by means of two-way analysis of variance and generalized linear models in repeated measurements. Bonferroni test was used as multiple comparison test. The level of statistical significance was set at $p \leq 0.05$.

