The Evaluation Of The Efficiency Of Micro- osteoperforation

Date :April 28, 2016

STUDY PROTOCOL

The aim of this study was to evaluate the effectiveness of micro-osteoperforations (MOP) performed in the alignment stage.

This was a 2-arm parallel-group, randomized, controlled trial with a 1:1 allocation ratio

The protocol of the study was approved by Izmir Katip Çelebi University Clinical Research Ethics Committee dated 18.05.2016 (no: 94) and T.C. Ministry of Health, Turkey Pharmaceuticals and Medical Devices Agency dated 09.09.2016 (document number: 228 418) was approved by decision.

Based on Mehr's (1) study, the dependent sample t-test using the G * Power 3.1 software program (Franz Faul, Universität Kiel, Germany) showed that 24 patients had an effect width of $d = 1.05$ and $\alpha = 0.05$ significance level. it was determined that the number of samples formed 80% power. Assuming a 15% exclusion rate, a total of 28 patients (14 patients) were included in the study.

The patients who applied to the Department of Orthodontics of the Faculty of Dentistry of Izmir Katip Çelebi University and who were found to comply with the study criteria were informed verbally and in writing. Written informed consent was obtained from patients and parents who agreed to participate in the study. A total of 28 patients (12 males and 16 females) aged between 12 and 27 years, with a diameter of more than 5 mm in terms of the Little irregularity index, were included in the study. The study groups were composed of 14 patients (4 boys, 10 girls) in the MOP applied (MOP+) group and 14 patients (8 boys, 6 girls) in the MOP not applied (MOP-) group.

The following inclusion and exclusion criteria were considered in the selection of patients to be treated: Inclusion Criteria:

- All permanent teeth have been removed (except the 3rd molars)
- Presence of more than 5 mm crowding in the lower arc according to Little irregularity index (1)

- Gingival and periodontal indices less than 1
- Good oral hygiene
- Patient and / or guardian volunteering to participate in the study
- Exclusion Criteria:
 - Congenital missing or pulled teeth
 - Severe skeletal malocclusion
 - Systemic disease
 - Presence of periodontal disease
 - Radiographic determination of bone loss

- Gingival pocket depth of more than 4 mm • Previous orthodontic treatment

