Table 1 presents the gender, age distribution and baseline Little irregularity index data of the patients. Table 1: Gender distribution by groups, mean age and perceptions.

GROUPS	MOP+		MOP-		TOPLAM		p
	n	%	n	%	n	%	

Female	10	71,46	42,9	16	57,10		
Male	4	28,68	57,1	12	42,90		
total	14	100	14	100	28	100	
	\bar{x}	ss	\bar{x}	ss	\bar{x}	ss	p
Little irregularity index	9,99	2,63	8,87	1,50	9,42	2,17	0,179
age (years)	17,21	3,76	15,29	1,77	16,25	3,05	0,095

n: number of individuals \bar{x} : average, ss: standard deviation, p<0,05

Oral hygiene procedures were explained visually with videos and applied on the model to all patients before the treatment and in the session where the brackets were applied. It was told that they should brush their teeth at least 3 times a day, then use an interface brush, pay attention to the foods that will cause caries and avoid acidic beverages. Periodontal status of the individuals included in the study before the treatment was evaluated with the help of periodontal measurements. Oral hygiene of the individuals included in the study was checked at each session and necessary suggestions were made.

The pre-treatment routine orthodontic recordings of the individuals included in the study were performed by taking plaster model, intraoral and extraoral photographs, panoramic and lateral cephalometric radiographs and evaluations according to inclusion criteria.

In each study, clinical periodontal parameters were measured with periodontal sonde just before (T0) and after the leveling (T1) treatment. Gingival thickness measurements were performed with an

ultrasonic device (Pirop® Ultrasonic Biometer A- Scan, Echo - Son, Krancowa, Poland).

In order to evaluate the changes in the dental arch until the leveling phase was completed, each session was taken from the lower jaw and plaster models were obtained. Afterwards, digital models were created from plaster models using 3D scanning device (3Shape R700 TM Scanner, Copenhagen, Denmark).

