With a 45 degree angle between the holding portion and the tip device, the conical tip 1.7 mm in diameter perpendicular to the teeth, without stressing the soft tissue, the measurement was carried out by applying to the mucosal outer surface. If the standard deviation of the 10 automatic mean values exceeds 0.05 mm, the gum thickness measurement was repeated.

Evaluation of Digital Model

In our study, nickel titanium (Ni-Ti, American Orthodontics, Sheboygan, WI, USA) wires were applied to the patients in appointments according to the current situation. Each session is used to record the current situation until the session in which 0.019x0.25 inch Ni-Ti wire is attached; T0 (start, n = 28), T1 (second session, n = 28), T2 (third session, n = 28), T3 (fourth session, n = 28), T4 (fifth session, n = 28), T5 (sixth session, n (MOP +) = 7, n (MOP -) = 9) plaster model was obtained from patients. In both groups, a smaller number of models were obtained in the T5, since some of the patients had previously inserted 0.019x0.25 inch Ni-Ti wire.

Plaster models were converted to digital models using a scanning device (3Shape R700 TM Scanner, Copenhagen, Denmark). Dental models were performed on digital models with the software program (OrthoAnalyzer TM, Copenhagen, Denmark).

In order to analyze changes in dental arches; Intermolar distance, intercanine distance, arc length, arc depth and Little perpendicularity index measurements were made in horizontal plane.

Points Used in Model Analysis

- 1) L6F (right and left): Central fossas of the lower molar teeth
- 2) L3T (right and left): Tuberule tips of the lower canine teeth
- 3) L6MCP (right and left): Mesial contact points of the lower molar teeth
- 4) L1-1CP: The intersection of the contact points of the lower central incisors
- 5) L1MCP, L2MCP, L3MCP: Lower central, lateral and canine tooth mesial contact points
- 6) L1DCP, L2DCP: Distal anatomical points of the lower central and lateral teeth

Measurements in Model Analysis

- 1) Intermolar distance: Distance between right and left L6F
- 2) Intercanine distance: Distance between right and left L3T
- 3) Lower arc length: Sum of the distance between the contact points of the lower incisors (L1-1CP) and the mesial contact points (L6MCP) of the right and left lower molars

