4) Lower arc depth: The distance between the intersection of the contact points of the lower incisors (L1-1CP) and the line connecting the mesial contact points (L6MCP) of the right and left lower molars.

5) Little irregularity index: Measure the distance between the teeth in the mandibular anterior region from the canine tooth's mesial (L3MCP) to the canine's mesial (L3MCP) on the other side with its own anatomical contact points (L1MCP, L2MCP, L1DCP, L2DCP) in the horizontal plane and add five measured values obtained (5).

Evaluation of Leveling Times

In assessing the leveling time in the lower jaw, the Little irregularity index was considered (5). The time from the beginning of treatment (T0) until the leveling was completed (T1: Little irregularity index falling below 1 mm) was calculated in days (6).

Evaluation of Pain and Patient Satisfaction During Treatment

A questionnaire was performed to assess pain and patient satisfaction at the beginning of treatment (T0), 1 hour later (T1), 12 hours later (T2), 7 (T3), 14 (T4) and 28 (T5) days (5). Visual analog scale (VAS) method was used for pain scoring, there is a range of 0–10, “no pain - unbearable pain” symbolizes information.

References

1. Mehr R. Efficiency of piezotome-corticision assisted orthodontics in alleviating mandibular anterior crowding—a randomized controlled clinical trial. 2013.
2. Propel orthodontics products-Treatment guide <https://www.propelorthodontics.com/wp-content/uploads/2015/01/Treatment-Guide.pdf> [
3. Bednarz W. The thickness of periodontal soft tissue ultrasonic examination—current possibilities and perspectives. *Dental and Medical Problems*. 2011;48(3):303-10.
5. Little RM. The irregularity index: a quantitative score of mandibular anterior alignment. *American journal of orthodontics*. 1975;68(5):554-63.

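### The SAP names no baseline covariate for leveling time, although the starting Little index is already measured and likely predicts it: a missed gain in precision, not an error

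*SAP*

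**What the plan says.** - **Endpoint.** The Protocol (Evaluation of Leveling Times) counts leveling time from the start of treatment "until the leveling was completed (T1: Little irregularity index falling below 1 mm) was calculated in days". The finish line is absolute and does not depend on where the patient began.
- **Analysis.** For between-group comparisons the SAP states: "Independent samples t test was used to compare the means between two independent groups of continuous measurements". For repeated measurements it states: "The comparison of the groups according to time was made by means of two-way analysis of variance and generalized linear models in repeated measurements". Neither sentence names a baseline covariate, and neither is tied to leveling time.
- **Baseline data.** The Protocol already reports them: "Table 1 presents the gender, age distribution and baseline Little irregularity index data of the patients". The Little index row reads "9,99 2,63 8,87 1,50 9,42 2,17 0,179" (MOP+ mean and SD, MOP- mean and SD, total mean and SD, p). Mean age is 17.21 (SD 3.76) years in MOP+ and 15.29 (1.77) in MOP-. The sex split is "14 patients (4 boys, 10 girls) in the MOP applied (MOP+) group and 14 patients (8 boys, 6 girls" in the MOP- group.
- **Planning effect.** The sample size text says "24 patients had an effect width of $d = 1.05", without saying which outcome this effect belongs to.

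**The concern.** A patient who starts further from 1 mm has further to go. On the Table 1 means, MOP+ must lose 9.99 - 1 = 8.99 mm and MOP- 8.87 - 1 = 7.87 mm, a ratio of 1.14. That gives a reason, within the documents, to expect the starting index to explain part of the spread in leveling time. An unadjusted t test leaves that part in the error term. With 28 patients, unused information of this kind can matter.

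The second strand is the observed difference at baseline. If a higher start lengthens leveling time, the unadjusted difference carries some of that handicap as though it belonged to the treatment. A null result would then be hard to read: no effect, or a harder starting point.

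**Working it through.** **Inputs.** Table 1 means and SDs; 14 patients per arm; alpha 0.05, taken as two-sided because the SAP does not say. Three inputs are assumptions: the correlation rho between baseline index and leveling time (range 0 to 0.7), a true benefit of 1.05 SD, and a continuous, normal outcome with a common linear slope.

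**Reproducing the plan's figures.**
- Little index: pooled SD = sqrt((2.63² + 1.50²)/2) = 2.141. Difference = 9.99 - 8.87 = 1.12 mm. t = 1.12/(2.141 x sqrt(2/14)) = 1.384 on 26 df, p = 0.178 against 0.179 printed. The 95% CI is -0.54 to 2.78 mm. Standardized difference g = 1.12/2.141 = 0.523.
- Age: pooled SD 2.939, difference 1.92 years, standardized difference 0.653, p = 0.096 against 0.095 printed.
- The 24 patients at d = 1.05 are recovered only as a one-sided independent t test (12 per arm, power 0.801). Two-sided with 14 per arm, the power is 0.76, which is the t-test figure used below.

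**Step 1: precision, averaged over randomizations.** Relative to the t test, the variance of the ANCOVA estimate is (1 - rho²) x (1 + 1/24); the second factor is the expected cost of estimating the slope with 26 within-arm df. At rho 0 the ratio is 1.04; at rho 0.5 it is 0.75 x 1.042 = 0.78. Break-even is rho² = 1/25, so rho = 0.20.

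**Step 2: shift given Table 1.** Other factors equal, the unadjusted difference moves against MOP+ by g x rho = 0.523 x rho SD. With g fixed, the variance ratio is (1 - rho²) x (1 + 0.523² x 7/26) = (1 - rho²) x 1.074, which breaks even at rho = 0.26.

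**Step 3: power by simulation** (40,000 trials per rho).

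| rho | Average: t test | Average: ANCOVA | Shift (SD) | Given Table 1: t test | Given Table 1: ANCOVA |
|---|---|---|---|---|---|
| 0 | 0.76 | 0.74 | 0 | 0.76 | 0.73 |
| 0.2 | 0.76 | 0.76 | 0.10 | 0.67 | 0.75 |
| 0.3 | 0.76 | 0.79 | 0.16 | 0.63 | 0.77 |
| 0.5 | 0.76 | 0.86 | 0.26 | 0.52 | 0.84 |
| 0.7 | 0.76 | 0.96 | 0.37 | 0.38 | 0.95 |

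The second decimal is approximate. The averaged columns are the ones that bear on a plan.

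**Step 4: no true effect.** Over randomizations both tests reject about 5% of the time. Given the Table 1 baseline and rho 0.5, the t test rejects 7.1% of the time, nearly always against MOP+; ANCOVA rejects 4.9%.

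**Step 5: age.** Treating the two effects as additive, the net shift against MOP+ is 0.523 x rho + 0.653 x r(age), where r(age) is the correlation of age with leveling time. It is zero at r(age) = -0.80 x rho. At rho 0.2 and r(age) -0.4 it is 0.105 - 0.261 = -0.16 SD, that is, toward MOP+.

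**Step 6: unequal slopes.** MOP+ carries 2.63²/(2.63² + 1.50²) = 75% of the within-arm baseline sum of squares, so it dominates the fitted slope. Take rho 0.5, arm slopes 0.25 and 0.75, and no effect at the midpoint baseline. The pooled slope is then 0.755 x 0.25 + 0.245 x 0.75 = 0.373. ANCOVA leaves 0.523 x (0.5 - 0.373) = 0.07 SD, against 0.26 SD unadjusted. Swapping the slopes changes only the sign.

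**The case against.** **The t test is valid.** This stands. Randomization protects it on average, and the baseline difference (p = 0.178) is within chance. A reader might infer that the SAP's analysis is wrong or biased by design; the documents do not support that. A non-significant imbalance can still shift this trial's estimate, but that is a statement about one allocation.

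**The covariate is picked because Table 1 looks uneven.** That would be a weak reason. The better one is the endpoint definition, which holds whatever Table 1 shows. It is also why the averaged figures come first, and these show no gain at rho 0.2 and about 3 points at 0.3.

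**The imbalance can only hide a benefit.** A reader might infer this from the higher start in MOP+. It does not follow: age and sex also differ, the documents do not say which way they act, and Step 5 shows a net shift toward MOP+ under assumptions no less plausible on the documents.

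**The model is too smooth.** This stands in part. Visits are monthly, so crossing 1 mm can be seen only at visits. The Protocol (Evaluation of Digital Model) lists "T1 (second session, n = 28), T2 (third session, n = 28), T3 (fourth session, n = 28), T4 (fifth session, n = 28", then 7 and 9 models at the sixth session. Few distinct leveling times are likely, although models stop at the final wire and not at the 1 mm threshold. The power figures do not reflect this coarse grid.

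**Leveling time is not named as primary.** True. It is one of five listed groups of variables, which limits the weight of the point.

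**Conclusion.** The point holds as a missed gain in precision for leveling time, not as an error. The averaged gain is about 10 points of power at rho 0.5 and 20 at 0.7; it is nil at about 0.2, and there is a loss of about 2 points at 0. Given the observed baseline, and other factors equal, the unadjusted difference is shifted against MOP+ by about 0.52 x rho SD. The net direction is not established, so neither a masked benefit nor the absence of a false one can be claimed.

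The size rests on an assumed rho, the 1.05 SD effect, and a normal outcome with a common slope. It cannot be put in days, because the documents give no SD for leveling time. The calculations do not cover the repeated index measurements, and no claim is made about them. Severity: optional, cheap improvement.

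**What to change.** - State in the SAP that leveling time is analysed with group plus baseline Little index as covariate: ANCOVA, or a time-to-event model with that covariate, which may suit the monthly visit grid better.
- Report the unadjusted result alongside.
- If the adjustment is chosen after Table 1 was seen, label it post hoc.
- Plot leveling time against baseline index by arm, so that the common slope can be judged.

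**Cost.** A sentence or two in the SAP, one degree of freedom and no new data. If rho is near zero, about 2 points of power are lost on average (0.74 versus 0.76), or 3 given the Table 1 baseline (0.73 versus 0.76). If the slopes differ by arm, the adjustment is incomplete, as in Step 6.

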In our study, bracketing was performed by using MBT system brackets (Mini Master Series® 2, American Orthodontics, Sheboygan, WI, USA) with 0.022x0.028 inch slots in both groups. After bracketing and before MOP administration, patients were asked to rinse their mouth twice with chlorhexidine mouthwash, each lasting for 1 minute. In the first session, MOP application was performed with Propel® (Ossining, NY, USA) driver under local anesthesia in the areas where the dental movement was requested in accordance with the manufacturer's instructions.

Propel® is a disposable device specially designed for micro-osteoperforation. The device includes a 1.5 mm thick perforation tip. It has a depth setting of 3, 5 and 7 mm and the LED depth indicator warns when the desired depth is reached. The device was removed from its sterile packaging and, after adjusting the desired depth, was gently placed on the gum and then turned clockwise with gentle pressure. When the desired skin was reached, the LED indicator was removed by turning it counterclockwise with the indicator illuminated. Micro-osteoperforations were performed directly and atraumatically in the keratinized gum at two or three points, 3 mm between canine canine, 5 mm between canine molar, and 7 mm deep in the posterior region and 1.5 mm in diameter in the alveolar bone (2).

In each group of patients using conventional fixed orthodontic braces, leveling with 0.014 inch nickel titanium (Ni-Ti, American Orthodontics, Sheboygan, WI, USA) arc wire was started. All patients were called for monthly visits and each session was measured and a plaster model was formed until the leveling phase was completed. Ni-Ti (American Orthodontics, Sheboygan, WI, USA) wires of 0.014 inch, 0.016 inch, 0.016x0.022 inch and finally 0.019x0.025 inch were used, respectively, depending on the leveling condition. In both groups, arc wires were connected to the slots by prefabricated steel wire ligatures.

In order to evaluate the clinical efficacy of micro-osteoperforation, the following variables were evaluated in both groups at the beginning of treatment and after completion of the leveling:

- Cephalometric measurements
- Periodontal measurements
- Amount of entanglement and width of tooth arch
- Leveling time
- Pain values and patient satisfaction

Evaluation of Hard and Soft Tissue Changes

Angular and linear measurements were performed on lateral cephalometric films taken at the beginning and after treatment.

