Lateral Cephalometric Radiography

The lateral cephalometric radiographs used in the study were taken with cephalometric x-ray device (Orthopantomograph, OP300, Scanora / Instrumentarium, Tuusula, Finland) in the Department of Oral

Diagnosis and Radiology of Izmir Katip Celebi University Faculty of Dentistry. Lateral cephalometric radiographs; natural head position, teeth in centric occlusion and lips in resting position. In order to perform cephalometric analysis, 24 points were determined and 9 cephalometric planes were created. A total of 13 measurements were performed using 4 skeletal, 6 dental and 3 soft tissues using Dolphin Imaging software (version 11.8, Dolphin Imaging, Chatsworth, CA, USA).

Cephalometric Points Evaluated in the Study

The points to be used for cephalometric analysis were grouped into 3 groups as skeletal, dental and soft tissue points.

Evaluation of Periodontal Tissues

Gingival index (GI), plaque index (PI), pocket depth (PD), probing bleeding (PB) and gingival thickness (GT) were measured when immediately before placing the bracket (T0) and after completion of the leveling procedure (T1) in all patients in the study. Periodontal measurements were performed by a single researcher in order to provide standardization. Probing was performed using the Williams periodontal probe (Hu Friedy®, Chicago, IL, USA) with a diameter of 0.5 mm and a guide line at 1-2-3- 5-7-8-9-10 mm on it to facilitate measurement. The measurements were recorded in clinical forms of each patient.

The gum thickness was measured using an ultrasonic measuring device (Pirop® Ultrasonic Biometer, A- Scan, Echo - Son, Krancowa, Poland) at the midline of the tooth, perpendicular to the tooth, in the middle of the keratinized gingival width (3).

Properties of Pirop® Biometer:

1. The device measures from 0.25 to 6 mm.
2. It shows sensitivity up to 0.01 mm.
3. It has an A-scan tip at a frequency of 20 MHz (4).

4. It transmits 10 ultrasonic waves to the application area and works on the principle of giving 10 gum thickness measurements by automatically calculating the distance traveled in mm as a result of the reflection of the ultrasonic waves from the hard tissue.

5. Automatically subtracts the average value from 10 measurements and reflects the results to the 5.7- inch LCD touch screen with standard deviation.

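### For outcomes measured only at baseline and at the end of leveling, the SAP does not say which test compares the arms, and no listed test adjusts for the baseline value

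*SAP*

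**What the plan says.** The trial is a parallel two-arm comparison with 14 patients per arm. Two families of outcomes have exactly two measurement times.

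- **Periodontal** (Protocol, Evaluation of Periodontal Tissues): gingival index, plaque index, pocket depth, bleeding on probing and gingival thickness "were measured when immediately before placing the bracket (T0) and after completion of the leveling procedure (T1) in all patients in the study".
- **Cephalometric** (Protocol, Evaluation of Hard and Soft Tissue Changes): "Angular and linear measurements were performed on lateral cephalometric films taken at the beginning and after treatment". The protocol's list of variables places the second assessment at the end of leveling. Under Lateral Cephalometric Radiography: "A total of 13 measurements were performed using 4 skeletal, 6 dental and 3 soft tissues".

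That makes 5 + 13 = 18 two-time outcomes.

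The SAP offers three kinds of test for continuous data:

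- "Independent samples t test was used to compare the means between two independent groups of continuous measurements"
- "dependent sample t test was used to compare two dependent groups"
- "The comparison of the groups according to time was made by means of two-way analysis of variance and generalized linear models in repeated measurements"

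It links none of these to a named outcome. It does not say whether the independent t test uses follow-up values or changes, and it names no covariate in any model.

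**The concern.** A paired test within one arm asks whether patients in that arm changed. It does not ask whether MOP made a difference. Some change in both arms is plausible for the gingival indices. Entry requires "Gingival and periodontal indices less than 1", so values start low and may rise under a fixed appliance whatever the arm. (This argument does not extend to cephalometry.) If one arm then crosses the significance threshold and the other does not, the table invites a conclusion about MOP that no test has addressed.

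The second issue is efficiency. Every patient has a baseline value for these outcomes, and with 14 per arm the intervals will be wide. A plan that leaves the deciding test open, and never uses baseline as a covariate, may report a wider interval than the data require. It also leaves the choice between follow-up values and changes to be made after the data are seen.

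**Working it through.** The plan gives no precision or power figure for these outcomes, so there is none to reproduce. The sample-size effect, d = 1.05, comes from a study of mandibular crowding and is not tied to periodontal or cephalometric measures. It is not used here; results are in standard deviation (SD) units.

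**Inputs.** n = 14 per arm (Protocol). Significance level 0.05 (SAP), taken as two-sided because the SAP does not say. Equal SD at both times, and the baseline-to-follow-up correlation r, are assumptions; r is shown over a range.

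**Step 1: what the repeated-measures analysis does.** With two times, the group-by-time term of the two-way ANOVA is the t test on change (F = t²). It compares the arms directly and uses the baseline value, with its coefficient fixed at 1.

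**Step 2: standard error of the arm difference**, with √(2/14) = 0.378 SD:

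- follow-up only: 0.378
- change: 0.378 × √(2(1 − r))
- ANCOVA: 0.378 × √(1 − r²)

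The ratio of ANCOVA to follow-up only is √(1 − r²). The ratio of ANCOVA to change is √((1 + r)/2).

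| r | SE follow-up | SE change | SE ANCOVA | cut v follow-up | cut v change |
|---|---|---|---|---|---|
| 0 | 0.378 | 0.535 | 0.378 | 0% | 29% |
| 0.3 | 0.378 | 0.447 | 0.361 | 5% | 19% |
| 0.5 | 0.378 | 0.378 | 0.327 | 13% | 13% |
| 0.7 | 0.378 | 0.293 | 0.270 | 29% | 8% |

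**Step 3: small-sample cost.** Estimating the slope inflates the ANCOVA variance by about 1 + 1/(28 − 4) = 25/24, or 2% on the standard error. The cuts at r = 0.3, 0.5 and 0.7 become about 3%, 12% and 27% against follow-up only, and 18%, 12% and 6% against change. ANCOVA breaks even with follow-up only where 1 − r² = 24/25, that is r = 0.2. It breaks even with change where (1 + r)/2 = 24/25, that is r = 0.92.

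**Step 4: detectable difference** (SD) at 80% power, noncentral t, with the 25/24 factor and 25 degrees of freedom for ANCOVA and 26 for the others:

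| r | follow-up | change | ANCOVA |
|---|---|---|---|
| 0 | 1.10 | 1.56 | 1.12 |
| 0.3 | 1.10 | 1.30 | 1.07 |
| 0.5 | 1.10 | 1.10 | 0.97 |
| 0.7 | 1.10 | 0.85 | 0.80 |
| 0.8 | 1.10 | 0.70 | 0.67 |

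**Step 5: discordant within-arm tests.** Let both arms have the same true change δ, in SDs of the change. The within-arm power p is that of a paired t test with 13 degrees of freedom and noncentrality δ√14. The chance that exactly one arm is significant is 2p(1 − p), and half of that is MOP+ alone.

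| δ | p | exactly one arm significant |
|---|---|---|
| 0 | 0.050 | 9.5% |
| 0.25 | 0.140 | 24% |
| 0.5 | 0.410 | 48% |
| 0.565 | 0.499 | 50% (maximum) |
| 0.75 | 0.737 | 39% |
| 1.0 | 0.932 | 13% |
| 1.25 | 0.991 | 2% |

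A simulation of 40,000 trials at δ = 0.5 and r = 0.5 gave 48.2% discordance. In the same simulation the direct t test on change and the follow-up-only t test each rejected 5.0% of the time. Both between-arm tests therefore keep their error rate.

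**The case against.** The strongest reply is that the SAP already contains a proper arm comparison. The group-by-time analysis uses the baseline value and is valid. A reader might infer that these outcomes are judged only by paired tests within arms and a t test that ignores baseline. The documents do not support that, because the SAP assigns no test to any outcome and its independent t test may itself be on change. That the paired test is meant for these outcomes is an inference. It is reasonable, since the digital models and the pain scores have many times and fit the repeated-measures analysis better, but the SAP does not say it.

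Three further points stand.

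- Nothing in the plan says that a conclusion on MOP will rest on discordant within-arm p-values. The 50% is the worst case of a possible misreading, not the error rate of a planned test, and it falls again if the common change is large.
- The gain from ANCOVA depends on an unknown r. Restricting entry to low indices tends to lower r for the gingival measures, so the 29% figure is least plausible there.
- A linear model may not suit bleeding on probing, whose scale the protocol does not define.

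What the reply does not remove is that the deciding analysis is unnamed and baseline is never a covariate.

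**Conclusion.** The point holds as under-specification with an avoidable loss of precision. It is not a finding of bias: follow-up and change comparisons are both valid under randomization. ANCOVA is the safer choice when r is unknown. Follow-up alone does poorly when r is high, change does poorly when r is low, and ANCOVA is close to or better than both across the range shown. Its disadvantage near r = 0 is slight (1.12 against 1.10 SD detectable). These sizes rest on equal SDs at the two times, roughly normal data, 14 patients per arm and the assumed correlations.

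The discordance figures, from 9.5% with no common change to at most 50%, apply only if within-arm p-values are read as evidence on MOP. The SAP does not prescribe that reading, but it does not rule it out.

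**What to change.** State in the SAP that, for each continuous two-time outcome, the arm comparison is an ANCOVA of the end-of-leveling value on arm and baseline value, reported as the adjusted difference with a 95% CI. If bleeding on probing is recorded as yes/no or as a count, use a matching generalized linear model with baseline as covariate. Present within-arm changes descriptively, and state that no conclusion on MOP is drawn from within-arm p-values. Name the time point in words, because the protocol's T1 label also denotes the second model session and the one-hour pain score.

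The cost is about two sentences and one degree of freedom per outcome, with the same data and software. The change does not address multiplicity across the 18 outcomes, which needs its own statement.

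### The SAP does not say whether T0 is an outcome or a covariate; read as an outcome, the 1.12 mm starting gap shifts the group effect and the change over time in opposite directions

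*SAP*

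**What the plan says.** The design is a "2-arm parallel-group, randomized, controlled trial with a 1:1 allocation ratio". Under Evaluation of Digital Model, the protocol lists the plaster-model sessions from the start of treatment: "T0 (start, n = 28), T1 (second session, n = 28"), then T2, T3 and T4 with 28 patients each, and a partial T5 (7 MOP+, 9 MOP-). The Little irregularity index and four arch measures are read from these models.

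On baseline values, "Table 1 presents the gender, age distribution and baseline Little irregularity index data of the patients". The index row reads "9,99 2,63 8,87 1,50" (mean and SD in MOP+, then in MOP-), with p = 0.179.

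For the longitudinal comparison the SAP says: "The comparison of the groups according to time was made by means of two-way analysis of variance". The same sentence adds generalized linear models in repeated measurements. The SAP does not say which variables or sessions enter, what role T0 has, whether there is a covariate, or whether the group main effect or the group-by-time interaction answers the question.

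**The concern.** T0 precedes treatment, so MOP cannot have affected it. If T0 is one of the levels of time, the group main effect averages in a session that carries only the starting gap, plus whatever part of that gap persists later. The change from T0 has the opposite problem. Both arms are being driven towards an index near zero, so the arm that starts higher has more millimetres to lose.

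With MOP+ starting higher, one term leans against MOP and the other towards it, even if MOP does nothing. A larger fall in MOP+ could be read as faster alignment when part of it is only the higher start. Because the SAP does not name the deciding term, the reader cannot tell which of two differently shifted figures is meant to be the result. This point concerns the session-by-session model data only. Leveling time in days is one value per patient and is not affected.

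**Working it through.** **Inputs.** From Table 1: MOP+ 9.99 (SD 2.63), MOP- 8.87 (SD 1.50), 14 per arm. From the protocol's model section: T0-T4 with n = 28 at each session. From Evaluation of Leveling Times: completion means an index below 1 mm. I take the Table 1 baseline to be the T0 model value. The documents give no later session means, slopes or residual SDs, so those below are assumptions.

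**1. The plan's own baseline figure.** Gap = 9.99 - 8.87 = 1.12 mm. Pooled SD = sqrt((2.63² + 1.50²)/2) = 2.14, so the gap is 0.52 SD. t = 1.12 / (2.14 × sqrt(2/14)) = 1.38 on 26 df, p = 0.178. The stated 0.179 agrees within rounding.

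**2. Shift with no MOP effect, if T0 is an outcome level.** Let b_k be the slope of session k on T0. Given the observed baselines, the expected arm difference (MOP+ minus MOP-) at session k is 1.12 × b_k. Therefore:

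- main effect over T0-T4 = 1.12 × (1 + b_1 + b_2 + b_3 + b_4)/5
- T4-minus-T0 contrast = -1.12 × (1 - b_4)

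| Assumed slopes at T1-T4 | Main effect (mm) | T4-minus-T0 (mm) |
|---|---|---|
| 0, 0, 0, 0 | 1.12 × 1/5 = +0.22 | -1.12 |
| 0.5, 0.25, 0.1, 0 | 1.12 × 1.85/5 = +0.41 | -1.12 |
| 0.69, 0.42, 0.23, 0.13 (proportional decline) | 1.12 × 2.47/5 = +0.55 | -0.98 |
| 0.8, 0.6, 0.4, 0.2 | 1.12 × 3/5 = +0.67 | -0.90 |
| 1, 1, 1, 1 (gap persists in full) | +1.12 | 0 |

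A positive value means more crowding in MOP+. A negative contrast means a larger fall in MOP+.

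**3. Can the gap persist in full?** Not to completion. Once every patient is below 1 mm, the arm means differ by less than 1 mm. The extra fall in MOP+ from T0 to completion must then lie between 1.12 - 1 = 0.12 mm and 1.12 + 1 = 2.12 mm, whatever MOP does. This bounds the change to completion, not to T4, but it makes the last row of the table implausible.

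**4. Simulation with Table 1 held fixed.** Assumptions: 50-65% of the index remains after each month, between-patient SD of the log rate 0.2 or 0.35, 15% measurement noise. With no MOP effect, the main effect is +0.44 to +0.57 mm and the extra T0-to-T4 fall in MOP+ is 0.91 to 1.04 mm. The formulas in step 2 give much the same:

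- retention 0.50: 1.12 × 1.94/5 = 0.43, and 1.12 × (1 - 0.06) = 1.05
- retention 0.65: 1.12 × 2.53/5 = 0.57, and 1.12 × (1 - 0.18) = 0.92

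**5. Rejection rates with no MOP effect, given this baseline.** With slopes below 1, the main effect rejects in 1.6-9.1% of runs. The interaction rejects in 6-12% uncorrected and 0.5-7% with the Greenhouse-Geisser correction. When the baseline is left random, the uncorrected interaction already rejects in about 9-11%, so most of that excess is non-sphericity and not the gap.

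**6. Power, if MOP speeds alignment 1.25-fold (set-up of step 4).** The main effect is about 0.0 mm and is significant in under 1% of runs. The corrected interaction rejects in 35-61%, and the T0-adjusted mean of T1-T4 in 30-70%.

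**7. After adjustment.** With T0 as a covariate and the mean of T1-T4 as outcome, the simulated arm difference with no MOP effect is -0.01 to +0.01 mm across the step 2 patterns. It rejects in 4.2-5.6% of runs.

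**The case against.** The SAP never says that T0 is an outcome level. The protocol's session list says when models were taken, not which of them enter the analysis, and the generalized linear models named in the same sentence could carry T0 as a covariate. This stands: what is established is silence plus a natural reading, not a stated wrong analysis.

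The imbalance is a chance one. Over repeated randomization the main effect is unbiased, and adjustment is ordinarily a gain in precision. This also stands. The conditional view still matters here, because the gap in this trial is already known and a non-significant p value does not remove it from the estimates.

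A reader might infer that a real MOP benefit would disappear from the ANOVA, or that false positives are likely. Steps 5 and 6 do not support either. The main effect near zero comes from a 25% effect that happens to cancel the gap: it is about +0.3 mm at 10%, -0.4 at 50% and -0.7 at 75%. A group-by-time interaction would usually be consulted, and with a standard sphericity correction its power is broadly similar to that of the adjusted analysis.

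The five-session interaction is also an omnibus test on 4 degrees of freedom and has no sign. The shift of 0.9-1.1 mm belongs to a T0-to-T4 contrast that the SAP does not name. That is fair. It applies to anyone who interprets the fall in millimetres, which an unsigned test invites.

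Finally, a model that keeps T0 as an outcome but forces a common baseline mean would handle the gap equally well. That is true, but the SAP does not specify one.

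**Conclusion.** The point holds as a gap in specification with a measurable consequence. The SAP leaves the role of T0 and the deciding term open and names no baseline adjustment. If T0 is an outcome level, the 1.12 mm gap moves the T0-T4 main effect by about 0.2-0.7 mm against MOP and the T0-to-T4 change by about 0.9-1.1 mm in its favour when MOP has no effect. The directions follow from the formulas for any later slopes between 0 and 1. The sizes rest on the assumed decline patterns and on the observed imbalance.

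The defect is in the estimates. The case for changing the plan is a single interpretable effect free of the starting gap, and not mainly control of type I error or a gain in power.

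**What to change.** In the SAP, for the Little irregularity index:

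- Take T0 out of the outcome. Analyse model sessions T1-T4 (n = 28 at each) by a repeated-measures model with arm, session, arm-by-session, T0 value and T0-by-session.
- Name the T0-adjusted arm difference averaged over T1-T4, with its 95% CI, as the MOP effect.
- Report the session-specific adjusted differences with 95% CIs beside it.

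The same form can be used for intercanine and intermolar distance, arc length and arc depth as ordinary baseline adjustment. The documents show no imbalance in those measures, so no shift is claimed for them.

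Cost: SAP wording and a re-run, with no new data. T0 takes one between-subject degree of freedom (28 - 2 = 26 falls to 25), and T0-by-session over four sessions takes 4 - 1 = 3 within-subject degrees of freedom. The adjustment assumes that later values are roughly linear in T0, which should be checked on a plot.
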